I understand my obligations as a clinical trial investigator and agree to perform and report the study in compliance with the protocol, Good Clinical Practice (GCP) and the current rules and regulations set forth by the applicable health authorities, regulations and the International Conference on Harmonization (ICH).

Name of investigator	Title	Signature	Date

Protocol Synopsis

I . Protocol title:

An Open-Label, Single-Arm Study of the Safety, Efficacy, and Pharmacokinetic Behavior of Leuprolide Mesylate for Injectable Suspension (LMIS 50 mg) in Subjects with Advanced Prostate Carcinoma – SAFETY EXTENSION

II . Objectives:

This is a Safety Extension study to Protocol FP01C-13-001. The primary objective of this study is to:

- Determine the safety and tolerability of LMIS 50 mg for up to 1 year under Protocol FP01C-13-001-EX (2 years of total exposure) in subjects with advanced prostate carcinoma;

III . Study drug:

1. Name: Leuprolide Mesylate for Injectable Suspension(LMIS)
2. Dosage form: Prefilled and supplied in one sterile syringe, ready-to-use
3. Dose: 50mg (as the mesylate salt)
4. Active ingredient: Leuprolide mesylate
5. Dosing schedule: 50 mg leuprolide mesylate administered subcutaneously, when given as two separate injections 6 months apart (Month 12 and Month 18 from the initiation of Protocol FP01C-13-001).

6. Mechanism of action:

The LH-RH agonist leuprolide, when given continuously, is known to inhibit pituitary gonadotropin secretion and suppress testicular and ovarian steroidogenesis. Serum testosterone concentrations in males have been reduced to levels associated with castration (≤ 50 ng/dL in serum). This effect is generally observed within two to four weeks after the start of treatment and is maintained as long as treatment continues. Induction and maintenance of castrate levels of serum testosterone concentrations in prostate cancer patients is a standard palliative treatment and slows cancer cell growth. LMIS 50 mg contains 50 mg leuprolide mesylate formulated in [REDACTED] and [REDACTED] to control and sustain the release of the bioactive leuprolide over a 6 month period after subcutaneous administration.

7. Pharmacological category: Antineoplastic agent, gonadotropin releasing hormone analog

IV . Developmental phase: phase I II IIIb IV Others

V . Study design:

1. Control: placebo
 active

 other  Uncontrolled

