5.1. Treatment plan summary

Subjects enrolled in this open-label, phase IIIb safety extension study will receive a single subcutaneous injection of LMIS 50mg every 6 months for up to 2 doses.

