5.4. Rationale for dose

The LMIS 50 mg dosage form has been developed to deliver bioactive leuprolide over a 6 month period after subcutaneous administration with a release profile similar to that of the Eligard® 45 mg formulation. The LMIS 50 mg dosage and its use as a sustained-release or depotdosage form have shown to be both efficacious and safe in similar leuprolide products (i.e. Eligard® 45 mg).

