9. EXTENT OF EXPOSURE AND DRUG COMPLIANCE

The treatment duration (days) is defined as (last administered date – first administered date + 1); and the study duration (days) is defined as (last visit date – first administered date + 1).

The treatment duration (days) and study duration (days) will be summarized by the number of observations (n), mean, median, standard deviation (SD), standard error, minimum and maximum. The summary results will be presented as Table 14.3.2. Also, the proportion of subjects received first and second administration has been provided as Table 14.3.2.

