10.3 Laboratory Evaluation

Clinical laboratory tests, including standard hematology, chemistry, and urinalysis:

Hematology

CBC, including Hb, Hct, RBC count, WBC count, WBC differential, platelet count and HgbA1c

Chemistry

ALT, AST, ALP, total bilirubin, BUN, Serum Cr, electrolytes (K, Na, Mg, Ca and P), blood glucose, lipid profile (LDL, HDL, triglycerides)

Urinalysis

pH, specific gravity, leukocyte, erythrocyte, protein

PSA Tumor Marker

PSA level

Testosterone Level

Testosterone level

Clinical laboratory data (hematology, biochemistry, and urinalysis) will be listed in Listings

Statistical Analysis Plan

16.2.8.2-16.2.8.4. Observations outside the normal range will be flagged. The abnormal values will be flagged with 'L' (low) for values below the lower limit of the laboratory's normal range or 'H' (high) for values above the upper limit of the laboratory's normal range. Clinically significant laboratory results will be marked as well. All original and repeated values will be listed.

The observed values of clinical laboratory data (hematology, biochemistry, and urinalysis) will be summarized for baseline, end of treatment, end of study, and change from baseline to end of treatment and end of study in Table 14.3.3.1~Table 14.3.3.3. Also, the clinical laboratory data transition status from baseline to end of treatment and end of study will be presented in Table 14.3.3.4~Table 14.3.3.6.

The PSA levels will be listed by subject in Listing 16.2.8.5; the testosterone level will be listed by subject in Listing 16.2.8.6.

Abnormal laboratory values of hematology, biochemistry and urinalysis will be listed in Listing 16.2.8.1.

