10.4 Vital Signs and Physical Examination

Individual subject listings of measured values for physical examinations, vital signs, and body weight data will be presented. The vital signs (blood pressure, heart rate, respiratory rate and body temperature) and body height, weight data will be presented in Listing 16.2.9, and physical examination will be presented in Listing 16.2.10, and the summary results of vital signs for baseline, end of treatment, end of study, and change from baseline to end of treatment and end of study will be presented as Table 14.3.4. In addition, the summary results of physical examination will be presented as Table 14.3.5.1, and the physical examination transition status will be presented as Table 14.3.5.2.

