System Organ Class 1	Preferred Term 2	E	nn	(xx.x%)	E	nn	(xx.x%)	E	nn	(xx.x%)	
System Organ Class 2	Preferred Term 1	E	nn	(xx.x%)	E	nn	(xx.x%)	E	nn	(xx.x%)	
System Organ Class 2	Preferred Term 2	E	nn	(xx.x%)	E	nn	(xx.x%)	E	nn	(xx.x%)	
Death AE											
System Organ Class 1	Preferred Term 1	E	nn	(xx.x%)	E	nn	(xx.x%)	E	nn	(xx.x%)	
System Organ Class 1	Preferred Term 2	E	nn	(xx.x%)	E	nn	(xx.x%)	E	nn	(xx.x%)	
System Organ Class 2	Preferred Term 1	E	nn	(xx.x%)	E	nn	(xx.x%)	E	nn	(xx.x%)	
System Organ Class 2	Preferred Term 2	E	nn	(xx.x%)	E	nn	(xx.x%)	E	nn	(xx.x%)	

E is the number of events, n is the number of subjects, and the AE percentage: 100%*The number of subjects with event (n) / Total number of subjects in Safety population (N)
[Program: \\Foresee\\FP01C-13-001\\SAP\\Table\\S_AE.sas]

Table 14.3.2: Summary of Study Medication (Safety Population)

Variables / Status	Total (N=XX)
Received first administration	
Yes	nn (xx.x%)
No	nn (xx.x%)
Received second administration	
Yes	nn (xx.x%)
No	nn (xx.x%)
Treatment duration (days)	
n	nn
mean (SD)	xx.x (xx.x)
SE	xx.x
median (min, max)	xx.x (xx.x, xx.x)
Study duration (days)	
n	nn
mean (SD)	xx.x (xx.x)
SE	xx.x
median (min, max)	xx.x (xx.x, xx.x)

Treatment duration (days) is defined as (last administered date – first administered date + 1); and study duration (days) is defined as (last visit date – first administered date + 1).
 [Program: \\Foresee\\FP01C-13-001\\SAP\\Table\\S_EX.sas]

Table 14.3.3.1: Summary of Laboratory Assessments - Hematology (Safety Population)

Variables / Status	Total (N=XX)
Hematology at Screening (V1)	
n	nn
mean (SD)	xx.x (xx.x)
SE	nn (xx.x%)
median (min, max)	xx.x (xx.x, xx.x)
Normal	nn (xx.x%)
Abnormal - NCS	nn (xx.x%)
Abnormal - CS	nn (xx.x%)
Not Done	nn (xx.x%)
Hematology on Day 168 (V4)	
n	nn
mean (SD)	xx.x (xx.x)
SE	nn (xx.x%)
median (min, max)	xx.x (xx.x, xx.x)
Normal	nn (xx.x%)
Abnormal - NCS	nn (xx.x%)
Abnormal - CS	nn (xx.x%)
Not Done	nn (xx.x%)
Hematology on Day 336 (V6/EOS)	
n	nn
mean (SD)	xx.x (xx.x)
SE	nn (xx.x%)
median (min, max)	xx.x (xx.x, xx.x)
Normal	nn (xx.x%)
Abnormal - NCS	nn (xx.x%)
Abnormal - CS	nn (xx.x%)
Not Done	nn (xx.x%)
Hematology change on Day 168 (V4)	
n	nn

*Paired T test or Wilcoxon signed rank test will be used to test the change from baseline for continuous variables.
 [Program: \\Foresee\\FP01C-13-001\\SAP\\Table\\S_LB.sas]

Table 14.3.3.1: Summary of Laboratory Assessments - Hematology (Safety Population)

Variables / Status	Total (N=XX)

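### SAP treatment duration stops at the last injection of a 6-month depot: 169 days for two on-schedule doses, 1 day for one dose

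*SAP*

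**What the plan says.** SAP section 9 defines the exposure measure: "The treatment duration (days) is defined as (last administered date – first administered date + 1". The footnote to Table 14.3.2 repeats it: "Treatment duration (days) is defined as (last administered date – first administered date + 1". The same section defines study duration as last visit date minus first injection date plus 1. Table 14.3.2 reports both durations and the proportions of subjects given the first and second injections.

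The product is a depot. The protocol synopsis (III.6, mechanism of action) says that the formulation is designed "to control and sustain the release of the bioactive leuprolide over a 6 month period after subcutaneous administration", and Protocol 5.4 says that it was "developed to deliver bioactive leuprolide over a 6 month period after subcutaneous administration". Protocol 5.1 gives the regimen as "a single subcutaneous injection of LMIS 50mg every 6 months for up to 2 doses". The objective in Protocol 2.1 and SAP 2 is safety over up to 1 year in the extension, for 2 years of total exposure.

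A related term appears in the safety sections. SAP 10.3 says that laboratory values "will be summarized for baseline, end of treatment, end of study, and change from baseline to end of treatment and end of study". SAP 10.4 plans "summary results of vital signs for baseline, end of treatment, end of study" and the corresponding changes. Neither section defines *end of treatment*. The table shells show visit days instead, for example "Hematology change on Day 168 (V4").

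**The concern.** Counting from first to last administration suits a drug taken daily, where exposure ends roughly when dosing ends. Here the last administration starts about 6 months of release. The formula therefore leaves out the final depot interval, and for a subject with one extension dose that interval is his whole exposure.

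Exposure is a core descriptive result in a study whose only aim is safety. The row headed treatment duration would show about half a year for a man who received everything planned, in a study set up to describe up to a year of treatment. It would show a single day for a man with one injection. One-dose subjects are foreseeable: the regimen is up to two doses, and Protocol 1.3 and 5.6 limit dosing to the shelf life of the supplied batch, with no guarantee of extension.

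**Working it through.** **Inputs**

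- Formulas for treatment and study duration: SAP 9 and the Table 14.3.2 footnote.
- Injection days: Day 0 and Day 168 ± 7 (Protocol 6.2 and 6.4). The schedule footnote foresees a late second injection.
- Last scheduled visit: Day 336 ± 7 (Protocol 6.6).
- Depot interval: the documents say 6 months and give no number of days. I assume 168 days, the spacing in the visit schedule, and show 183 days as the calendar alternative.

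The plan prints no duration value, so there is no figure to reproduce, only a rule to apply.

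**Step 1: the SAP rule, on schedule**

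- Two doses: 168 − 0 + 1 = 169 days. Within the window: 161 − 0 + 1 = 162 to 175 − 0 + 1 = 176. A delayed second injection gives more than 176.
- One dose: 0 − 0 + 1 = 1 day.

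**Step 2: nominal coverage**, (last injection day − first injection day) + interval

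| | SAP rule | Coverage, 168-day interval | Shortfall | Coverage, 183-day interval | Shortfall |
|---|---|---|---|---|---|
| Two doses | 169 | 336 | 167 | 351 | 182 |
| One dose | 1 | 168 | 167 | 183 | 182 |

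**Step 3: coverage capped at the subject's latest known date**, min(last injection day + 167, latest date) − first injection day + 1

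| Subject | Capped coverage | SAP rule | Shortfall |
|---|---|---|---|
| Doses on Days 0 and 168, last date Day 336 | min(335, 336) + 1 = 336 | 169 | 167 |
| Doses on Days 0 and 175, last date Day 336 | min(342, 336) + 1 = 337 | 176 | 161 |
| Doses on Days 0 and 168, last date Day 252 | min(335, 252) + 1 = 253 | 169 | 84 |
| One dose, last date Day 336 | min(167, 336) + 1 = 168 | 1 | 167 |
| One dose, last date Day 84 | min(167, 84) + 1 = 85 | 1 | 84 |

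**Step 4: can study duration stand in?**

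- On-schedule completer: 336 − 0 + 1 = 337 days against 336 covered. Yes.
- One dose, last visit at Day 84: 84 − 0 + 1 = 85 days, taking a telephone contact as not a visit. The protocol asks for telephone contacts at 3 and 6 months after the last injection. If the 6-month contact is made, coverage is 168 days.
- One dose, followed to Day 336: 337 days against 168 covered.

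For one-dose subjects, study duration can therefore be too short or too long.

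**Step 5: effect on the reported mean**

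The share p given a second dose is not in the documents, so it is varied. All dosing is taken as on schedule, with nobody leaving before the depot interval ends. The SAP mean is 1 + 168p and the nominal coverage mean is 168 + 168p.

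| p | SAP mean (days) | Coverage mean (days) |
|---|---|---|
| 1.00 | 169 | 336 |
| 0.90 | 152.2 | 319.2 |
| 0.75 | 127 | 294 |
| 0.50 | 85 | 252 |

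**Step 6: the term *end of treatment***

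The laboratory shells show Screening, Day 168 (V4) and Day 336 (V6/EOS). The vital-sign shell uses Day 0 as baseline for blood pressure, heart rate, temperature and respiratory rate, with the same two later visits. With Day 336 marked as end of study, Day 168 is the only visit left for *end of treatment*. Protocol 6.4 takes the Day 168 vital signs, blood and urine before the second injection.

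**The case against.** The definition is explicit and is printed under the table, so nobody is misled about what was calculated, and no number in the documents is wrong. The same table gives study duration and the proportion receiving each dose, and Listing 16.2.5.2 gives every dose date. For completers, exposure can be read from what is planned.

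Most of that stands. This is a choice of definition, not a slip in arithmetic, and for completers the table largely repairs it. It does not repair it for subjects with one dose or an early exit, as step 4 shows. A row titled treatment duration, under extent of exposure, should not need that reconstruction.

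A reader might also infer that the row merely repeats the second-administration row. It does not: it carries the actual gap between injections, and late second doses will spread it.

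Nor do the documents support the inference that readers of the results will mistake Day 168 for the outcome of full treatment, or Day 336 for off-treatment follow-up. The shells print visit days, both visits are summarised, and nothing labels Day 336 as post-treatment. What remains is an undefined term in SAP 10.3 and 10.4 that does not match the shells.

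**Conclusion.** The point holds as a minor defect in one descriptive row. The rule leaves out the last depot interval: 169 days against nominal coverage of 336 for two on-schedule doses, and 1 against 168 for one dose. This rests on a 168-day interval; at 183 days the nominal coverage is 351 and 183.

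The 167-day shortfall is the nominal case. It would be tempting to apply it to every subject, but once coverage is capped at last contact or death it falls, for example to 84 or 161 days in step 3. The mean shortfall therefore depends on the share given a second dose and on early departures, neither of which the documents give.

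It would also be tempting to conclude that safety rates will be wrong by a factor of about two. The documents do not support that. No patient-year rate is planned, and AE percentages use the number of subjects in the Safety population. Newly treatment-emergent AEs run until the subject is off study, so they are not cut at the last injection.

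**What to change.** In SAP 9 and the Table 14.3.2 footnote, replace the definition with:

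treatment duration = min(last injection date + 167, latest of last visit, last contact or death for that subject) − first injection date + 1.

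State the 168-day depot interval as the assumption, and add the number of injections received to Table 14.3.2. The formula counts any gap before a late second injection as covered; a footnote should say so.

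All dates are already planned: visit and last-contact dates in Listing 16.2.1, injection dates in Listing 16.2.5.2, and telephone-contact and death dates in Listing 16.2.13. Listing 16.2.13 is needed because the last-contact field in Listing 16.2.1 follows the item on subjects unable or unwilling to return, and may be filled only for them.

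As a secondary wording change, replace *end of treatment* in SAP 10.3 and 10.4 with Day 168 (before the second injection), so that the text matches the shells.

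The cost is one derivation, one added row and one relabelling in the SAP. It needs no protocol amendment and no new data, and it changes no planned test or AE percentage.

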10. SAFETY ANALYSIS

10.1 Adverse Events

All AEs (whether treatment related or not) that occur before, during, or after dosing of the study medication will be recorded. The verbatim adverse event (AE) terms will be coded using the MedDRA dictionary, version18.1 or highest, and classified by System Organ

Statistical Analysis Plan

Class and Preferred Term.

Adverse events will be categorized as:

- Previous treatment-emergent adverse event (TEAE): The TEAEs are captured from previous FP01C-13-001 study.
- Newly treatment-emergent adverse event (TEAE): AEs occurring during or after the treatment period until the subject is off study, or before the first administration of study drug and worsen in severity for this FP01C-13-001-EX study.

Total treatment-emergent adverse event (TEAE): The combination of previous TEAEs and Newly TEAEs.

Unless otherwise specified, all adverse event summaries will include the previous TEAEs, Newly TEAEs and Total TEAEs. The listing of all TEAEs will be provided in Listing 16.2.7.1.

All AEs will be summarized by CTCAE version 4 grade and MedDRA preferred terms. The severity will be graded as follows:

- Grade 1 Mild; asymptomatic or mild symptoms; clinical or diagnostic observations only; intervention not indicated
- Grade 2 Moderate; minimal, local or noninvasive intervention indicated; limiting age-appropriate instrumental activities of daily living* (ADL)
- Grade 3 Severe or medically significant but not immediately life-threatening; hospitalization or prolongation of hospitalization indicated; disabling; limiting self-care ADL**
- Grade 4 Life-threatening consequences; urgent intervention indicated
- Grade 5 Death related to AE

Activities of Daily Living (ADL):

*Instrumental ADL refer to preparing meals, shopping for groceries or clothes, using the telephone, managing money, etc.

**Self-care ADL refer to bathing, dressing and undressing, feeding self, using the toilet, taking medications, and not bedridden.

The reasonable possibility of causation will be determined based on the investigator's clinical judgment as follows:

- **Definite:** A clinical event, including laboratory test abnormality, occurring in a plausible time relationship to drug administration, and which cannot be explained by concurrent disease or other drugs or chemicals.
- **Possible:** A clinical event, including laboratory test abnormality, with a reasonable time sequence to administration of the drug, but which could also be explained by concurrent

Statistical Analysis Plan

disease or other drugs or chemicals. Information on drug withdrawal may be lacking or unclear.

- **Unrelated:** A clinical event, including laboratory test abnormality, which is clearly not related to drug administration.

For purposes of the summary tables, AEs will be classified as either related or not related to study drug. A study drug-related AE is defined as any TEAE that is assessed as 'Definite' or 'Possible' to study drug. An AE not related to study drug is defined as any AE that is assessed as 'Unrelated' to study drug.

Frequency counts will be tabulated and displayed by the MedDRA System Organ Class and Preferred Term.

A general summary of all TEAEs will be provided in Table 14.3.1.1. This summary will present the numbers and percentages of subjects according to the following categories:

- TEAEs
- TEAEs by severity
- TEAEs by relationship
- Drug-related AEs
- Drug-related AEs by severity
- SAEs

Other summary tables for adverse events will include:

Table 14.3.1.2: Summary of Incidence of TEAEs

Table 14.3.1.3: Summary of Incidence of TEAEs by Severity

Table 14.3.1.4: Summary of Incidence of Drug-Related Adverse Events

Table 14.3.1.5: Summary of Incidence of Drug-Related Adverse Events by Severity

The additional tables of AEs with incidence rate >5% are provided as Table 14.3.1.7~ Table 14.3.1.10. In addition, TEAEs leading to discontinuation will be provided in Listing 16.2.7.2.

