(10) Record any pre-treatment AE(s) NOTE: Open AEs from Protocol FP01C-13-001 will be recorded in this study file and noted in the database and other study documentation as, "AE under Protocol FP01C-13-001." These AEs should not be counted twice in the overall safety database.

*If the patient completed 12 months of treatment with LMIS 50 mg more than 28 days prior to entering the Extension study, the testosterone level should be repeated and the repeat test should indicate that the patient maintains a castrate-level of testosterone. In addition, the ECOG, PE, ECG, laboratory and PSA tests should be repeated.

If the patient has completed 12 months of treatment with LMIS 50 mg under Protocol FP01C-13-001 within the last 28 days, they will be allowed to enter the Extension study without repeating the testosterone measurements, ECG, PE, laboratory and the PSA tests.

6.2. Day 0 (approximately 6 months from last dose of LMIS 50 mg under Protocol FP01C-13-001)

Perform the following at 0 hr:

- (1) Record subject enrollment number prior to dosing (same enrollment number as was used in FP01C-13-001 will be used in this study)
- (2) Record vital signs prior to dosing
- (3) Record concomitant medication(s) prior to dosing
- (4) Record AE(s) prior to dosing and post dosing
- (5) Administer LMIS 50 mg.

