10.2 Serious Adverse Event

A SAE is any experience that suggests a significant hazard, contraindication, side effect or precaution. With respect to human clinical experience, this includes any event which:

- results in death
- is life-threatening
- requires inpatient hospitalization or prolongation of hospitalization, unless

Statistical Analysis Plan

hospitalization is for:

- routine treatment or monitoring of the studied indication, not associated with any deterioration in condition.
- elective or pre-planned treatment for a pre-existing condition that is unrelated to the indication under study and has not worsened since the start of study drug
- treatment on an emergency outpatient basis for an event not fulfilling any of the definitions of a SAE given above and not resulting in hospital admission
- social reasons and respite care in the absence of any deterioration in the subject's general condition
- results in persistent or significant disability/incapacity or
- is a congenital anomaly/birth defect
- is a significant or important medical event that, based on appropriate medical judgment, may jeopardize the subject or may require intervention to prevent one of the other outcomes listed above.

A listing of all serious adverse events and serious adverse events report will be provided in Listing 16.2.7.3, and the summary of SAEs will be presented as Table 14.3.1.6.

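### SAP 10.1: the Total TEAE column can miss adverse events that start between the parent study's last visit and extension Day 0 (minor, and only if parent AE collection stopped at that visit)

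*SAP*

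**What the plan says.** SAP 10.1 sets up three groups.

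- Previous: "The TEAEs are captured from previous FP01C-13-001 study".
- Newly: "AEs occurring during or after the treatment period until the subject is off study, or before the first administration of study drug and worsen". The worsening must be of severity and must happen within the extension.
- Total: "Total treatment-emergent adverse event (TEAE): The combination of previous TEAEs and Newly TEAEs".

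The shells of Tables 14.3.1.1 to 14.3.1.10 have these three columns and no other.

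Collection is wider than classification. SAP 10.1 says that AEs "that occur before, during, or after dosing of the study medication will be recorded". Protocol 6.1, item 10, has the site record pre-treatment AEs at Screening, and only events still open from the parent study are labelled as parent-study events. The schedule marks adverse events in both Screening columns.

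Three other statements matter. On relatedness: "A study drug-related AE is defined as any TEAE that is assessed as" Definite or Possible (SAP 10.1). On the general listing: "The listing of all TEAEs will be provided in Listing 16.2.7.1". On serious events: "A listing of all serious adverse events and serious adverse events report will be provided in Listing 16.2.7.3" (SAP 10.2).

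On timing, Protocol 6 puts Day 0 about 6 months after the last parent dose, and Protocol 6.1 puts Screening at Day -28 to 0 from the parent end-of-study visit. Inclusion criterion 1 (Protocol 4.1) also admits men more than 28 days after that visit, with a repeat testosterone test and no stated maximum interval. Table 1 gives these men their own Screening column.

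**The concern.** Leaving out a pre-dose event that does not worsen is the usual convention for men who have not yet been treated, and it is right for Newly. Total is a different kind of column. It joins two studies of the same depot in the same men and will be read as their cumulative experience on LMIS. Men in the interval between the studies are not untreated. The product is designed to release over 6 months (Synopsis III.6), and a man who enters more than 28 days late must still be castrate at Screening (Protocol 4.1, criterion 1).

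An event in that interval can therefore be recorded, and even be judged drug-related by the investigator, yet have no column. Because drug-related AEs are defined as a subset of TEAEs, it is absent from the drug-related tables too. If it is serious, it is absent from the counts in Table 14.3.1.6.

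**Working it through.** No figure in the plan is at issue, so the check applies the SAP 10.1 definitions case by case. Let g be the days from the parent end-of-study visit to extension Day 0.

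Assumption: parent AE collection ended at that visit. Neither document gives the parent AE window.

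| Onset | Worsens in the extension? | Previous | Newly | Total |
|---|---|---|---|---|
| TEAE up to the parent end-of-study visit | no | yes | no | yes |
| TEAE up to the parent end-of-study visit | yes | yes | yes | yes |
| After that visit, before Day 0 | no | **no** | **no** | **no** |
| After that visit, before Day 0 | yes | no | yes | yes |
| From Day 0 on | either | no | yes | yes |

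One row has no home. It is empty when g = 0 and can be filled whenever g > 0.

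Could an event that starts in the gap and is still ongoing at Day 0 count as occurring during treatment? That reading would leave the separate pre-dose clause, which demands worsening, with no work to do. The literal result stands.

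Direction of the error in Total: the event count E loses every such event. The subject count n falls only if the man has no other event in that row of the table; otherwise n is unchanged. Both can only be too low or unchanged.

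Size: the documents do not give the number of men with a gap, the gap lengths or the AE rates. What can be shown is the share of one man's two-study period that falls in the gap:

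share = g / (P + 336 + g),

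where 336 days is the scheduled extension (Table 1) and P is the length of the parent study, described only as 12 months and assumed here to be 336 to 365.25 days.

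| g (assumed, days) | P = 336 | P = 365.25 |
|---|---|---|
| 0 | 0% | 0% |
| 14 | 14/686 = 2.0% | 14/715.25 = 2.0% |
| 28 | 28/700 = 4.0% | 28/729.25 = 3.8% |
| 60 | 60/732 = 8.2% | 60/761.25 = 7.9% |

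These are shares of calendar time for a man with that gap. They are not AE counts, and they say nothing about how many men have such a gap.

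**The case against.** The strongest reply is that the hole depends on something outside the documents. Previous means whatever the parent study captured. If its AE window ran up to Day 0, the hole closes; if it ran partly into the interval, the hole shrinks. That stands, and the point is conditional on it.

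Second, the schedule plans almost no gap. That also stands: only men with a real delay are affected, and among their events only those that do not worsen. But late entry is provided for in the inclusion criteria and the schedule, so the gap is not hypothetical.

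Third, the stated objective is safety over up to 1 year in the extension, with 2 years of total exposure in parentheses, and Newly answers the first part. A reader might infer that the extension's main safety result is understated. It is not, because Newly is untouched.

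A reader might also infer that gap events vanish from the report altogether. The documents do not support that. Serious ones are in Listing 16.2.7.3. SAP 10.1 describes Listing 16.2.7.1 as a listing of TEAEs, but its shell is titled Adverse Events and shows no such restriction. SAP 10.1 also promises that all AEs will be summarised by grade and preferred term, and Protocol 10.3 tabulates AEs without a treatment-emergent filter. The plan is ambiguous about the listing. None of this gives the event a place in Total, since the table shells have only the three columns.

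**Conclusion.** The point holds as a minor, conditional one. If parent AE collection ended at the parent's last visit, the literal SAP 10.1 definitions leave events that start in the gap and do not worsen out of Total, including its drug-related and SAE counts. Total can then be too low for men with a non-zero gap.

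The size is unknown, and it is zero for any man whose Day 0 falls on his parent end-of-study date. It is tempting to multiply the 137 men named in SAP 4.3 by an assumed gap and AE rate to get a number of lost events. The documents do not support that: 137 is a ceiling on enrolment, and neither a gap length nor an AE rate is given. No claim is made about rates per unit of time.

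**What to change.** Change the SAP only.

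1. In SAP 10.1, define Total TEAE as any AE with onset or worsening from the first parent LMIS injection to extension end of study, each event counted once. Counting once matters because a parent event that worsens in the extension meets both existing definitions.
2. Leave Previous and Newly as they are. Show gap-onset AEs that are not already Newly as a between-study category, included in Total in Tables 14.3.1.1 to 14.3.1.10, so that the drug-related and SAE tables are covered.
3. State that Listing 16.2.7.1 lists all recorded AEs.
4. Add to Table 14.3.2 the days from the parent end-of-study visit to Day 0 (n, mean, SD, median, minimum, maximum). The interval from the last parent injection would not serve, since it is about 6 months even with no gap.

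No protocol amendment is needed, because pre-treatment AEs are already recorded at Screening. Onset dates are already in the AE listing shell, and the ten AE table shells that carry the column all name the same program. The cost is one changed definition, one extra column that will be mostly empty if gaps are short, and one derived variable that needs the parent visit date. A limit remains: gap events in late entrants are recalled at Screening, so mild ones may be under-reported.
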